Attentional Control Scale (ACS)³³: The ACS a 20-item self-report instrument in the NIH Toolbox⁶⁶ that measures participants' perceived ability to (a) focus on relevant stimuli while ignoring distractors (e.g., "My concentration is good even if there is music in the room around me"), and (b) shift attention (e.g., "After being interrupted or distracted, I can easily shift my attention back to what I was doing before"). The ACS will be administered at the clinical assessment visits (baseline, mid-treatment, post-treatment, and 3-month follow-up) as well as weekly during the therapy visits.

Attentional Engagement-Disengagement Task (AEDT)⁴⁰: The AEDT will be used as a behavioral measure of attentional control. Two emotional faces are presented (happy, disgusted, and sad paired with neutral faces; Radboud Faces database)⁶⁷ and eye tracking is measured; 72 trials. Half of trials measure (a) *attentional engagement* with emotional expressions (i.e., once participants fixate on the neutral face, a frame around the emotional face indicates they should shift their gaze), and the other half measure (b) *attentional disengagement* (i.e., shifting from emotional to neutral). Gaze latency (i.e., time to fixation) is the main outcome. This task has been linked to rumination⁶⁸ and is sensitive to treatment.⁶⁹ It is expected that individuals with RNT will display delayed disengagement (i.e., longer time to fixation) when shifting from negative to neutral stimuli (vs. from positive to neutral or from neutral to emotional)³⁷⁻³⁹, which is expected to improve with ERT-AR. Eye movements will be recorded using a Tobii Pro X3-120 (described in "Equipment" below). The AEDT will be administered at the following timepoints: baseline (week 0), mid-treatment (week 4), and post-treatment (week 8). Computer task sessions will occur within a 7-10-day window, but no longer than 14 days from each clinical assessment visit.

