Perseverative Thinking Questionnaire – Past Week (PTQ-PW)⁸²: The PTQ-PW is a 15-item self-report measure of transdiagnostic repetitive negative thinking within the past week. Items on the PTQ-PW are independent of disorder-specific content and inquire about thoughts as repetitive, intrusive, unproductive, and capturing mental capacity (e.g., “The same thoughts keep going through my mind again and again”). The PTQ-PW is our primary outcome measure. It will be administered at the screening visit to determine eligibility (PTQ-PW \geq 37), the assessment visits (baseline *if more than 7 days has passed since screening*, mid-treatment, post-treatment, and 3-month follow-up), and weekly during the therapy visits.

Disorder-specific presentations of RNT will additionally be captured via the following measures, which will each be collected at the clinical assessment visits (baseline, mid-treatment, post-treatment, and 3-month follow-up):

Penn State Worry Questionnaire (PSWQ)⁸³: The PSWQ is a 16-item self-report scale that measures the tendency to engage in excessive, uncontrollable, generalized worry (e.g., “I am always worrying about something”).

Rumination Response Scale (RRS)⁸⁴: The RRS is a 22-item self-report questionnaire that measures participant general responses to sad or depressed mood (e.g., “think about how sad you feel.”).

Rumination on Obsessions and Compulsions Scale (ROCS)⁸⁵: The ROCS is a 33-item self-report measure that assesses the frequency of various responses (e.g., “I distract myself with anything that comes to mind”) to intrusive thoughts or images in the past month.

Symptom Measures

The following gold-standard interview measures will be administered by the IE at the clinical assessment visits (baseline, mid-treatment, post-treatment, and 3-month follow-up) to assess OCD, GAD, and depression symptom severity respectively:

Yale-Brown Obsessive Compulsive Scale (Y-BOCS)^{86,87}: This 12-item rater-administered semi-structured scale includes a checklist of common obsessions and compulsions and rates severity (distress and impairment) of OCD symptoms over the past week.

Structured Interview Guide for the Hamilton Anxiety Rating Scale (SIGH-A)⁸⁸: The SIGH-A is a 19-item structured, clinician-administered rating scale that provides an overall measure of generalized anxiety in the past week.

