Randomization

At the baseline visit, eligible subjects will be randomized (1:1 in parallel) to AR-ERT or SPT using the REDCapTM database.

Treatment

For all participants, treatment will consist of 8 weekly sessions provided via Healthcare Secure ZoomTM that are 60 minutes in duration. Eight sessions is the length of ERT currently being tested,^{107,108} allowing us to directly compare our effect sizes with the full package. All sessions are individual treatment (no group treatment).

Attention Regulation – Emotion Regulation Therapy (AR-ERT)

A brief, manualized version of individual Emotion Regulation Therapy (ERT) focused on the Attention Regulation module will be administered to patients randomized to AR-ERT. Specifically, the 8-session protocol will be a streamlined version of ERT, which tested as part of a NIH-sponsored R34:MH070682. The full protocol^a engages several active mechanisms (i.e., attention regulation, metacognitive regulation, reward/threat processing) and an 8-session version of this full treatment is currently being studied; however, in order to test the target of attentional/cognitive control, we are focusing solely on attention regulation skills: (a) Orienting (i.e., the ability to flexibly shift attention) via mindfulness of the breath (sessions 1-4), and (b) Allowing (i.e., the ability to sustain attention despite unpleasant emotional experiences) via mindfulness of thoughts and emotions (sessions 5-8). Treatment will also include lessons for practicing these skills in two different contexts: (a) reactive: reviewing challenging (i.e., emotion-laden) situations that have happened in the past week in which attention regulation skills could have been applied to counter automatic reactive RNT responses (sessions 1-4) as well as (b) proactive: preparing for challenging situations that may happen in the future in which skills could be implemented (sessions 5-8).

Specifically, session 1 provides patients with a model of how RNT maintains emotions, presents between-session self-monitoring of RNT, and introduces the attention regulation skill of Orienting via mindfulness of the breath. In sessions 2-4, Orienting skills continue to be practiced. Patients review their self-monitoring forms to detect triggers and consequences of RNT. They also conduct in-session imaginal rehearsal of situations from the past week that

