Emotional Control Task (CECT) and during the resting-state period (0.1-100Hz, sample rate = 256Hz) using established procedures,¹²³ and gross artifacts will be rejected by visual inspection. For the CECT, cue- and target-locked event related potentials (ERPs) will be formed by segmenting EEG data around cue and stimulus onsets (from -200 ms to 1000 ms post-stimulus) and averaging the segments. Start and end points for the components of interest are: (a) cue-locked N2: 200-350ms post-cue; (b) target-locked N2: 200-350ms post-target; (c) target-locked N450: 400-500ms post-target; (d) target-locked P300: 300-600ms post-target.⁴⁹ ERPs will be rejected if there is significant artifact (e.g., amplitude $\pm 100 \mu\text{V}$) at any electrode on a given trial. Artifact-free mean amplitudes (μV) will be extracted for ERP analyses. Additionally, nonoverlapping, artifact-free 2-second epochs from the resting-state period will be extracted for source localization analyses. Building on recent source localization studies,^{80,124} seeds from key regions within the frontoparietal (FPN) and default mode (DMN) networks will be selected to create regions of interest (ROIs) based on previous published methods^{125,126} and drawing from the Montreal Neurological Institute 305 template.¹²⁷ We will then compute EEG source-based functional connectivity using exact Low Resolution Electromagnetic Tomography (eLORETA) software.⁷⁸

Primary Analyses

Due to the nested structure of the data (i.e., 4 assessments per participant), we will use a multi-level generalized linear modeling (GLM) approach to address each of our hypotheses.

Hypothesis 1: Target Engagement. To test whether participants who receive AR-ERT show greater improvements in attentional/cognitive control relative to those who receive SPT, we will run a series of GLM analyses for each index of our attentional/cognitive control target:

- 1) **Behavioral:** (a) attentional disengagement (i.e., latency of shift in gaze from emotional to neutral face surrounded by the frame; AEDT), and (b) sustained attention (i.e., difference in reaction times to tones following a negative vs. neutral stimulus on the EIT),

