- 2) **Electrophysiological:** (a) proactive cognitive control in anticipation of conflict (i.e., cue-locked N2 ERP amplitudes on “opposite” vs. “actual” trials; CECT), and (b) reactive cognitive control in response to conflict (i.e., target-locked N2, N450, and P300 ERP amplitudes after the “opposite” vs. “actual” cue; CECT),
- 3) **Self-report:** Attentional Control Scale (ACS).

We will analyze each target index individually without adjusting for multiple testing¹²⁸ in order to be inclusive in identifying targets for future studies (e.g., R61/R33 proposal). Analyses will be modeled as the GLM equivalent of 2 x 3 ANOVAs with treatment condition (AR-ERT vs. SPT), time (pre-, mid-, post-treatment), and their interaction as fixed effects; the primary contrast of interest will be treatment difference at week 8 (post-treatment).¹²⁹ Repeated measures per person will be modeled with either an auto-correlation, Toeplitz, or unstructured covariance matrix (choosing the best model based on AIC and BIC).

Hypothesis 2a: Treatment Efficacy. To examine whether repetitive negative thinking (RNT) and psychiatric functioning improve during AR-ERT, we will also use GLM. Analyses will be modeled as the GLM equivalent of 2 x 4 ANOVAs with treatment condition (AR-ERT vs. SPT), time (pre-, mid-, post-treatment, follow-up), and their interaction as fixed effects; the primary contrast of interest will be treatment difference at week 8 (post-treatment), and a secondary outcome contrast will be at week 20 (3-month follow-up). Outcomes include:

- 1) **Repetitive Negative Thinking:** (a) Perseverative Thinking Questionnaire – Past Week (PTQ-PW; primary outcome), (b) Rumination Response Scale (RRS), (c) Penn State Worry Questionnaire (PSWQ), and (d) Rumination on Obsessions and Compulsions Scale (ROCS).

- 2) **Clinical Symptoms:** (a) Yale-Brown Obsessive Compulsive Scale (Y-BOCS) and Dimensional Obsessive-Compulsive Scale (DOCS), (b) Structured Interview Guide for the Hamilton Anxiety Rating Scale (SIGH-A) and State Trait Anxiety Inventory-Trait (STAI-T), (c) Structured Interview Guide for the Hamilton Depression Rating Scale (SIGH-D) and Beck Depression Inventory (BDI-II), and (d) Clinical Global Impression Scale – Severity (CGI-S).
- 3) **Psychiatric Functioning:** (a) Work and Social Adjustment Scale (WSAS), and (b) Quality of Life Enjoyment and Satisfaction Questionnaire – Short Form (Q-LES-Q-SF).

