In prior studies,^{31,140} ERT significantly improved mean levels of attentional control (ACS, our self-report target; 15.6%) and reduced RNT (PTQ-PW, our primary outcome; 37.2%) from pre- to post-treatment; with effect sizes of Hedge's $g = 1.65$ and 2.36 respectively in an open trial. ERT also significantly reduced worry (PSWQ; 34.8%) and rumination (RRS; 17.6%); with effect sizes of Hedge's $g = 1.50$ and 0.74 respectively compared to a waitlist control group with contact. Our electrophysiological and behavioral targets of attentional/cognitive control have also demonstrated sensitivity to intervention in previous studies.^{40,77,141} Sixty-two patients with elevated RNT (to balance power with recruitment feasibility) will enter the study to have a sample of 52 with attrition, which is reasonable given previous 85% retention rates of ERT at post-treatment (our primary endpoint).³¹ Based on power calculations (i.e., one-way ANOVA at post-treatment, assuming a 1:1 randomization to AR-ERT vs. SPT), with $n = 52$ completers, we will have 80% power to see a difference at .05 sig. level if the true effect size is 0.8 or greater

which is within range of the previous studies cited above. Finally, with 52 people at the end of treatment, we can detect correlations between target and outcome measures of .38 or greater.

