- c) As part of the informed consent process, participants will be asked if they are willing to provide contact information for two friends or family members and to give permission to have the research team call or write to these individuals in the case of an emergency (i.e., if we have concerns about their wellbeing).
 - d) Suicidality will be closely monitored with the BDI-II suicide item (#9) and clinician inquiry at each visit.
 - e) Patients at higher risk will be withdrawn from the study as described in the next section below.
 - f) [name] (or covering clinician in her absence) will be available 24/7 to participants in the event of a clinical emergency; this will be clearly communicated orally and in writing to study participants (i.e., the consent form describes how to reach the investigators in an emergency). Participants will be referred for a higher level of care as needed.
 - g) In the event that a study staff member witnesses behaviors such as abuse or neglect of children or the elderly while conducting a virtual study visit via Zoom™, they will report this to the PI who will consult with the Office of General Council and follow hospital policy for reporting such behaviors.
- 7) **Participant Withdrawal.** Subjects may be withdrawn from the study for *any* of the following reasons:
- a) A significantly deteriorating clinical course, such as emergence of active suicidal ideation or a need for hospitalization.
 - b) Score of ≥ 2 on the BDI-II suicide item (#9) and subsequent evaluation by the PI indicating it would be unsafe for the patient to remain in the study.
 - c) Score of 6 (much worse) or 7 (very much worse) on the CGI-I for 3 consecutive weeks and therapist and PI judgment that remaining in the study is not in the subject's best interest; a patient may be withdrawn sooner than this, if in the judgment of the therapist and PI, this is in the patient's best interest.
 - d) PIs' decision that withdrawal from the study is in the subject's best interest.
 - e) Subject's decision to withdraw.

Subjects who require medication changes or begin other types of therapy (e.g., family therapy) will be kept in the study even though such events violate study procedures. We will compare outcome data for compliant and non-compliant subjects.

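### Weekly PTQ-PW and ACS scores are collected but not modelled, so a patient who worsens, stops before week 4 and misses the later assessments enters the analysis with baseline alone

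*Combined protocol and SAP*

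**What the plan says.** Section 5 (Study Procedures) schedules PTQ-PW at screening, at baseline if more than 7 days have passed, and then at "mid-treatment, post-treatment, and 3-month follow-up), and weekly during the therapy visits". ACS is given at the clinical assessments "as well as weekly during the therapy visits". In both arms "treatment will consist of 8 weekly sessions", so up to three session scores can exist before the week 4 visit.

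Section 6, Primary Analyses, starts from the scheduled visits: "Due to the nested structure of the data (i.e., 4 assessments per participant), we will use a multi-level generalized linear modeling (GLM) approach". The Hypothesis 1 model, which covers ACS, has "time (pre-, mid-, post-treatment), and their interaction as fixed effects". The Hypothesis 2a model, which covers PTQ-PW, has "time (pre-, mid-, post-treatment, follow-up), and their interaction as fixed effects". Both take the week-8 treatment difference as the primary contrast. No part of section 6 brings the weekly scores into a model, an imputation or a sensitivity analysis.

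Section 6, Missing Data, relies on the model to keep all participants in an intent-to-treat analysis whatever is missing. It commits to missingness patterns and reasons by arm, a search for factors associated with dropout, and sensitivity analyses with no method named. It also says that scheduled assessments will be attempted in withdrawn subjects. Section 7, Participant Withdrawal, repeats this for everyone except those who withdraw consent. The same section lists as one ground for withdrawal "Score of 6 (much worse) or 7 (very much worse) on the CGI-I for 3 consecutive weeks", combined with therapist and PI judgment, and allows withdrawal sooner.

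Section 6, Power Analysis, says that 62 patients "will enter the study to have a sample of 52 with attrition".

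**The concern.** A likelihood model that includes every randomised patient is unbiased only if missingness depends on scores that are in the model. Here one stated route to withdrawal acts on what happens between modelled visits. The patient rates the CGI-I at each therapy visit, so three consecutive poor ratings can be reached by session 3, before week 4. If that patient provides no later assessment, the model holds one score, baseline, and nothing that marks the patient as different from those who stayed. Loss that could be missing at random given the weekly scores is not so given the scheduled ones.

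At stake are the week-8 estimate for the primary outcome and that for one of the Hypothesis 1 target indices. The issue is confined to these two: AEDT, EIT, CECT, PSWQ, RRS and ROCS have no weekly scores.

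**Working it through.** **1. The plan's own figures.** 52/0.85 = 61.2, rounded up to 62; 62 × 0.85 = 52.7. With 26 per arm and a standardised difference of 0.8, two-sided 0.05, noncentral-t power is 80.7%. The detectable correlation at n = 52 is 0.380. All reproduce, and nothing below changes them. The plan allows for 62 − 52 = 10 patients lost by week 8 (16%), from any cause and at any time.

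**2. What the model does with a baseline-only record.** It takes E[Y8 | Y0] = μ8 + β(Y0 − μ0), with μ8 and β learned from patients still observed. With session scores it would take E[Y8 | Y0, Y1, Y2, Y3].

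One-patient example, assuming a linear 0.8 SD arm improvement, baseline at the arm mean and three assumed covariance settings: a patient rising 1 SD by week 3 is predicted at −0.80 SD from baseline alone, and at −0.18 to +0.04 SD from the weekly scores. The gap of 0.62 to 0.84 SD, spread over 31 patients, moves the arm mean by 0.020 to 0.027 SD.

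**3. Effect on the contrast.** The documents give no SDs, correlations or dropout timing, so these inputs are assumptions: intercept variance 0.45, slope variance over 8 weeks 0.35, residual variance 0.20 (week-8 SD = 1); linear change; SPT improves 0.8 SD. Patients with the worst mean change over weeks 1–3 have no score after week 3. The estimate is maximum likelihood with arm × time and unstructured covariance, 200,000 simulated patients per arm. Entries are the week-8 benefit of AR-ERT over SPT in SD.

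| Lost, AR-ERT / SPT | True benefit | Nothing missing | Weeks 0, 4, 8 only | All weekly scores |
|---|---|---|---|---|
| 5% / 0 | 0.80 | 0.794 | 0.840 | 0.794 |
| 10% / 0 | 0.80 | 0.798 | 0.883 | 0.798 |
| 16% / 0 | 0.80 | 0.799 | 0.925 | 0.798 |
| 10% / 5% | 0.80 | 0.796 | 0.834 | 0.796 |
| 10% / 10% | 0.80 | 0.796 | 0.797 | 0.797 |
| 16% / 16% | 0.80 | 0.803 | 0.804 | 0.804 |
| 0 / 10% | 0.80 | 0.802 | 0.717 | 0.802 |
| 16% / 0 | 0 | 0.000 | 0.127 | 0.000 |

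In a 31-patient arm, 5%, 10% and 16% are about 2, 3 and 5 patients.

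**4. Hand check of the 10% / 0 row.**
- Early change has variance 0.35/16 + 0.20/3 + 0.20 = 0.2885 (SD 0.537). The worst 10% average 1.755 SD above its mean.
- Their baseline deviates by −0.20/0.537 × 1.755 = −0.65.
- Their week-8 score deviates by (0.35 × 0.25)/0.537 × 1.755 = +0.29.
- Baseline alone predicts (0.45/0.65) × (−0.65) = −0.45, a shortfall of 0.74.
- Bias ≈ 0.74 × 0.10/0.90 = 0.082, against 0.085 simulated.

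**5. At trial size (31 per arm, 3,000 runs).** With a true benefit of 0.80, the scheduled-only bias is 0.884 − 0.804 = 0.080 at 10% / 0 and 0.914 − 0.792 = 0.122 at 16% / 0. With weekly scores it is 0.001 or less. The standard error is about 0.26 under either model, and 0.127/0.26 = 0.49. A separate simulation at 31 per arm, with 25% against 5% loss and assumed covariances, cut the contrast bias from 0.06–0.07 to under 0.005 SD, with the standard error essentially unchanged at 0.22–0.23.

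**6. When loss does not follow the recorded scores.** With the same variances, 15% loss and log-odds of 1 to 2 per SD, the bias in one arm's mean falls from 0.038–0.069 to 0.020–0.038 SD if loss depends on the current, unrecorded score. It falls from 0.034–0.061 to 0.026–0.046 SD if loss depends on underlying worsening. Weekly scores then remove about a quarter to just under half of the bias.

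**The case against.** The strongest reply is that stopping therapy is not the same as leaving the study. Sections 6 and 7 both seek the remaining assessments, with payment, and only those who withdraw consent are exempt. A patient withdrawn by staff for deterioration is in contact with the team and will be asked to continue. This stands, and it limits the point to patients who also miss the later assessments. That group need not be empty: the plan allows for 10 patients without a week-8 score, and because the mid- and post-treatment assessments may be combined with therapy visits, stopping one can mean missing the other.

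A reader might infer that the treatment effect is inflated in favour of AR-ERT. The documents do not support that. Section 7 names temporary distress from exercises that belong to AR-ERT, but adds that significant distress is rare. Nothing shows more worsening-related loss in that arm. Equal loss leaves the contrast unbiased, and loss in SPT alone understates the benefit.

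Nor are all 10 expected losses affected, only those who leave early after worsening.

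The near-zero bias with weekly scores also depends on loss following those scores. The withdrawal rule acts on CGI-I and clinical judgment, so step 6 may be nearer the truth.

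Finally, analysing scheduled visits uniformly across outcomes is defensible, and sensitivity analyses are promised. They are not specified, however, and describing attrition by arm does not correct the estimate.

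**Conclusion.** The point holds in a limited form. For PTQ-PW and ACS the plan leaves unused the scores that would show early worsening in patients with no later scheduled assessment. Each arm's own improvement is overstated when such patients exist. The week-8 contrast is biased only if this loss differs between arms, in either direction. Under the assumed covariances the size is about 0.05 to 0.13 SD for 5% to 16% lost from one arm and none from the other, about 0.04 SD for 10% against 5%, and about 0 for equal loss. The worst case is about half a standard error in a trial powered for 0.8 SD. This does not undermine the design. It is an inexpensive improvement and should be settled before the data are seen, since deciding later whether to use the weekly scores would leave discretion over the primary result.

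**What to change.** Add to section 6, under Missing Data and Hypotheses 1 and 2a, wording to this effect:

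*For PTQ-PW and ACS, missing mid- and post-treatment scores will be multiply imputed by arm, with baseline and the weekly session scores up to the last session attended as auxiliary predictors. The treatment × time model and the week-8 contrast will then be fitted as specified. The number of patients with no scheduled score after baseline will be reported by arm.*

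An equivalent option is to enter the weekly scores as extra response occasions in the likelihood model, leaving the week-8 contrast unchanged. That needs a parsimonious covariance: baseline, eight sessions and week 20 make 10 occasions, or 10 × 11/2 = 55 unstructured parameters for 62 patients.

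The cost is SAP wording and modest programming. The downside is a larger model at 31 per arm. It may need a reduced set of weekly predictors, such as the last score and the slope, which may remove less of the bias. No gain in standard error is expected. Because worsening not reflected in the recorded scores is only partly handled, the sensitivity analysis promised under Missing Data should also be named, with its missing-not-at-random assumption stated.

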2. SPECIFIC AIMS

Primary Aim

Aim 1: Demonstrate target engagement with AR-ERT.

- **Hypothesis 1:** By enhancing attention regulation skills, AR-ERT will improve the biobehavioral target of attentional/cognitive control from pre- to post-treatment relative to a supportive psychotherapy (SPT) control group as measured by multi-method indices:
 - a) Behavioral: disengagement and sustained attention in the presence of emotional stimuli as measured by eye tracking fixations and reaction time,
 - b) Electrophysiological: proactive and reactive cue- and target-locked N2, N450, and P300 ERPs in a cued conflict monitoring task, and

- c) Self-report: perceived ability to shift and focus attention.

Secondary Aim

Aim 2: Assess if alteration in the hypothesized target is related to improvements in clinical outcomes (i.e., target validation).

- **Hypothesis 2a:** AR-ERT will improve RNT (transdiagnostic and disorder-specific measures) and psychiatric functioning (OCD, GAD, MDD symptoms; functional impairment) from pre- to post-treatment relative to SPT, with gains maintained at 3-month follow-up.
- **Hypothesis 2b:** Improvements in pre/post attentional/cognitive control will be associated with pre/post improvements in RNT and psychiatric functioning.

Exploratory Aim

We will use source localization to investigate neural generators of ERPs and resting state functional connectivity, with a focus on the default mode and frontoparietal networks.

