6. BIOSTATISTICAL ANALYSIS

Overview

Data acquisition and analytics approaches will be performed by [name] under the supervision of biostatistician [name]. To characterize our sample, data will be displayed graphically, and summary statistics (e.g., means and frequencies) will be calculated for all variables, including demographic and clinical descriptors. Descriptive statistics and exploratory graphing (e.g., scatter plots) will be used to assess normality, skew, and outliers on all measures. Continuous measures will be transformed if necessary, to satisfy assumptions of normality and homogeneity of variance.

Baseline differences between the treatment arms (AR-ERT vs. SPT) in demographic and other potential prognostic variables will be examined using chi-square analyses for discrete variables and ANOVA for continuous variables. While randomization tends to produce well-balanced treatment samples, if we find significant differences in potentially important baseline variables, we will include these variables as covariates in subsequent multivariate analyses. Candidate covariates for adjustment include baseline values of RNT (PTQ-PW score), symptom measures (Y-BOCS, SIGH-A, SIGH-D), and use of psychotropic medication (yes/no). Additional covariates that are unlikely to moderate treatment effect, but nonetheless will be examined for completeness, include: age, gender, education, race/ethnicity (majority vs. minority as we do not anticipate recruiting enough subjects from any one minority group to perform analyses for specific groups). If effects of gender and/or minority status are found that might be clinically meaningful, even if not statistically significant, we will report these to guide future research. Frequencies of adverse events (with 95% confidence intervals) will be calculated by treatment arm and type of event. We also will compare treatment groups on baseline credibility/expectancy of treatment and post-treatment satisfaction. A two-tailed p value $<.05$ will be considered evidence of statistical significance for the primary outcome.

Missing Data

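### The primary week-8 contrast has no pre-specified adjustment for each outcome's own baseline; it is unbiased, but less precise than it could be at no cost

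*Combined protocol and SAP*

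**What the plan says.** Section 6, Primary Analyses, sets out the Hypothesis 1 model as treatment condition, "time (pre-, mid-, post-treatment), and their interaction as fixed effects; the primary contrast of interest will be treatment difference at week 8 (post-treatment". Hypothesis 2a has the same form with four time points and the same week-8 primary contrast. Neither paragraph mentions a common baseline mean, a baseline covariate or a difference-in-change contrast. The Hypothesis 1 contrast carries a citation (reference 129) to a paper on analysing pre-post designs, without saying what is taken from it.

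The hypothesis itself is worded as change: "AR-ERT will improve the biobehavioral target of attentional/cognitive control from pre- to post-treatment relative to a supportive psychotherapy (SPT) control group" (Section 2, Hypothesis 1).

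Section 6, Overview, is the only place where baseline adjustment appears. The arms are compared on baseline variables, and those that differ significantly become covariates. The named candidates are baseline PTQ-PW, Y-BOCS, SIGH-A, SIGH-D and psychotropic medication use, with demographic variables examined for completeness. Baseline ACS, AEDT, EIT and ERP values are not named.

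Section 6, Missing Data, keeps all participants in the model whether or not they have missing visits.

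Section 6, Power Analysis and Sample Size, rests on a "one-way ANOVA at post-treatment, assuming a 1:1 randomization to AR-ERT vs. SPT".

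**The concern.** A treatment effect plus a full treatment-by-time interaction, with pre-treatment as one of the times, gives every arm-by-time cell its own mean. In such a model the week-8 contrast draws nothing from the baseline when nobody is missing. If one arm happens to start higher, that imbalance carries into the week-8 estimate in proportion to the pre-post correlation.

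The significance-triggered rule is a weak safeguard. It leaves smaller imbalances alone, it makes the form of the primary model depend on the data, and its named candidates leave out all the Hypothesis 1 outcomes. For PTQ-PW it would also enter the week-0 value as a covariate in a model that already treats week 0 as a response.

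At stake is precision in a trial of 62 participants with 52 expected at week 8. The planned detectable effect of 0.8 is large for a comparison with an active control, and the effect sizes quoted in support come from an open trial and a waitlist comparison.

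**Working it through.** **Inputs from the documents**
- Two-sided 5% level: "A two-tailed p value $<.05$ will be considered evidence of statistical significance for the primary outcome".
- Target: "we will have 80% power to see a difference at .05 sig. level if the true effect size is 0.8 or greater".
- Sample: 62 "will enter the study to have a sample of 52 with attrition", justified by "previous 85% retention rates of ERT at post-treatment" (62 × 0.85 = 52.7). With 1:1 allocation this is 26 per arm at week 8.

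**Assumed input.** The documents give no correlation ρ between baseline and week 8. I use 0.2 to 0.7.

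**Step 1: the plan's own figure.** A two-group one-way ANOVA is a two-sample t test with 50 df.
- SE in SD units: √(2/26) = 0.277.
- Noncentrality: 0.8/0.277 = 2.88; critical t = 2.009.
- Power = 80.7%; detectable difference at 80% power = 0.79.

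The stated 80% is reproduced.

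**Step 2: what the listed model estimates.** I compared generalised least squares variances for the model with separate week-0 means and the model with a common week-0 mean, under compound-symmetry and AR(1) covariance. With 31 per arm and complete data, the separate-means model has exactly the variance of the raw week-8 difference (ratio 1.000 under both structures). The common-mean model has 1 − ρ² times that variance.

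**Step 3: size of the gain.** Variance factor 1 − ρ², 26 per arm, 49 df, so noncentrality is 2.88/√(1 − ρ²).

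| Assumed ρ | Variance reduction | SE reduction | Power at 0.8 | Detectable difference |
|---|---|---|---|---|
| none (as planned) | – | – | 80.7% | 0.79 |
| 0.2 | 4% | 2% | 82.3% | 0.78 |
| 0.3 | 9% | 5% | 84.2% | 0.76 |
| 0.5 | 25% | 13% | 90.4% | 0.69 |
| 0.7 | 49% | 29% | 97.7% | 0.57 |

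The formula leaves out the small cost of estimating the baseline slope. A simulation of 62 patients gave variance ratios of 0.86, 0.76 and 0.66 at ρ = 0.4, 0.5 and 0.6, against 0.84, 0.75 and 0.64 by formula.

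**Step 4: planned dropout.** With 31 per arm, 5 of them missing week 8, the separate-means model already recovers some information from dropouts' earlier visits: 2% to 10% of the raw completers' variance over ρ = 0.3 to 0.7. The common-mean model's variance relative to it is 0.92 (ρ = 0.3), 0.78 (0.5) and 0.54 to 0.55 (0.7). At ρ = 0.5 the gain is therefore about 22%.

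**Step 5: what the significance trigger misses.** With 31 per arm, a baseline difference reaches p < .05 only at 2.00 × √(2/31) = 0.51 SD. At ρ = 0.5, an imbalance just short of this shifts the week-8 estimate by 0.5 × 0.51 ≈ 0.25 SD, about a third of 0.8 (0.25/0.8 = 0.32).

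**Step 6: is the quantity estimated the wrong one?** In a simulation with a true effect of 0.8, the raw week-8 difference averaged 0.798 and the difference in change 0.799. A pure change contrast has 2(1 − ρ) times the raw variance: 1.4 at ρ = 0.3, 1.0 at 0.5, 0.6 at 0.7. It is more precise than the raw contrast only if ρ exceeds 0.5.

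**The case against.** Four stronger readings are tempting, and the documents do not support them.

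- **That the contrast fails to test the hypothesised change.** Allocation is randomised, so the expected week-8 difference equals the expected difference in change (Step 6).
- **That chance imbalance biases the result or inflates type I error.** It does neither; the unadjusted test's 5% error rate already allows for chance imbalance. What remains is lost precision, and an estimate that can be off in a particular trial where the arms happened to start apart.
- **That the baseline contributes nothing.** The conditional covariate rule uses it, and so does the mixed model for participants who miss week 8. Both uses are partial.
- **That a quarter of the precision is lost.** That is a variance figure at ρ = 0.5, which the documents do not supply. It is 13% on the SE scale, and about 22% of variance once dropout is modelled.

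Two further objections carry weight. Several Hypothesis 1 indices are within-task differences (EIT negative minus neutral, ERP opposite versus actual), whose pre-post correlation is unknown and may be low. At ρ = 0.1, power rises only to 81.1%. The PTQ-PW entry cut-off of 37 may lower ρ for that scale too. So the gain will differ by outcome and could be negligible for some.

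It can also be argued that the cited pre-post reference implies a common baseline. Its content is not available here. The plan does not say that it adopts one, and the terms it lists give each arm its own week-0 mean. If a common baseline was intended, the wording needs correcting in any case.

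**Conclusion.** The point stands as a question of efficiency and pre-specification. As written, the primary contrast for Hypotheses 1 and 2a is the raw week-8 difference when data are complete. Adjustment is left to a significance test, and its named candidates omit the Hypothesis 1 outcomes. The contrast is valid, and the power statement is correct for it and would be conservative under adjustment.

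The avoidable variance is 4% to 49% for assumed ρ of 0.2 to 0.7. The detectable difference could fall from 0.79 to between 0.78 and 0.57. These figures assume equal variances, a linear baseline relation and 26 per arm at week 8. This is a recommended improvement; it corrects no invalid analysis.

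**What to change.** For every Hypothesis 1 and 2a outcome, pre-specify one of the following and take the week-8 contrast (and week 20 for Hypothesis 2a) from it:

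1. The same longitudinal model with week-0 means constrained equal across arms, i.e. time effects plus treatment effects at post-baseline visits only.
2. Post-baseline visits as responses, with the outcome's own baseline and baseline-by-time as covariates.

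Use this in place of the significance-triggered covariate rule in Section 6, Overview. Any further covariates should be fixed in advance. Say what, if anything, is taken from reference 129. For PTQ-PW and WSAS, state that the screening value serves as week 0 when the scale is not repeated at baseline.

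The cost is SAP wording only. Table 1 already schedules a baseline value for every outcome concerned, so no participants, visits or measures are added, and the sample size need not change.
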